5.5.7 VISIT 2-0, DISPENSE PAIR #2

This visit is subsequent to Visit 1-3.

Assessments of Pair #2 will be conducted as described for Pair #1 at visit (Visit 1-0).

5.5.8 VISIT 2-1 OPTIMIZE PAIR #2

Participants will be asked to insert study lenses at least 2 hours prior to the visit.

This visit will occur 3-10 days (inclusive) after visit 2-0.

Assessments of Pair #2 will be conducted as described for Pair #1 at visit (Visit 1-1).

5.5.9 VISIT 2-2 DISPENSE (OPTIMIZED) PAIR #2

This visit may be subsequent to Visit 2-1 (if no prescription change is needed) or is scheduled after Visit 2-1.

Assessments of Pair #2 will be conducted as described for Pair #1 at visit (Visit 1-2).

5.5.10 VISIT 2-3, 1-MONTH FOLLOW-UP PAIR #2

Participants will be asked to insert study lenses at least 2 hours prior to the visit.

This visit will occur 28-32 days (inclusive) after visit 2-2.

Assessments of Pair #2 will be conducted as described for Pair #1 at visit (Visit 1-3).

Participants will be asked to complete a 'Preference questionnaire' to compare between Lens Pair #1 and Lens Pair #2.

5.5.11 EXIT VISIT

The study exit form will be completed when a participant exits the study. This form will be completed either at study completion, or if the participant is discontinued from the study at another time. A study exit form must be completed for all participants who have taken a study ID number. If in the opinion of the investigator post-study follow-up visits are required, the exit form will be completed after the last follow-up visit.

Exit visual acuity will be recorded with either the participant's spectacles, refraction or habitual contact lenses. An exit biomicroscopy assessment will be conducted if not already completed on the same day for a concurrent study visit.

After the exit assessments have been completed, the participant and investigator will complete the study completion and remuneration forms. At this time the participant will be considered as having exited the study.

5.5.12UNSCHEDULED VISITS

An unscheduled visit is defined as an interim visit requested by the participant or investigator due to an unanticipated problem. Data recorded at these visits will be entered into the database. Only relevant and applicable unscheduled visit information will be included in the final report as deemed necessary.

5.6 STUDY PROCEDURES

Table 4 summarizes the procedures conducted at each visit.

Table 3: Summary of procedures to be conducted at scheduled visits

	0	1-0	1-1	1-2	1-3, 2-0	2-1	2-2	2-3	Exit
	Screen Fit of BOTH study CLs	Dispense Pair #1	Optimize Pair #1	Dispense optimal Pair #1	1-month follow-up Pair #1 & Disp. Pair	Optimize Pair #2	Dispense optimal Pair #2	1-month follow-up Pair #2	
C	V				#2				
Consent process Subject age, sex,	X								
race, ethnicity	^								
CL history and/or	Х		Х		Х	Х		Х	
lens wear schedule									
Health & medication	Х	Х	Х	Х	Х	Х	Х	Х	
Review any		Х	Х	Х	X	Х	Х	X	
problems with									
eyes/study lenses									
	Х								X (or subj. refraction)
	Х								
	X								
	X								
Study lens fit assessment &/or	X	X	X	X	X	X	X	X	
power optimization									
Dispense study CLs		X		X	X		X		
	X (except intermed VA)	x	x	x	x	X	x	x	
				X			X		
					х			х	
					x			X	
								Х	
	Х	Χ*	Х	Χ*	X	Х	Χ*	Х	
Study completion						-			X
and Exit									

^{*} Not required if visit concurrent subsequent to previous one.

¹ High Contrast High Illumination

5.6.1 STUDY LENS FITTING

Both lens types will be fit according to the manufacturers fitting guide, using the vertex-corrected spectacle refraction as a guide. Learnings from the first lens fit will not be applied to the second lens fit because it is of interest to determine how many lenses were needed to achieve the final lens prescription.

5.6.2

5.6.3 LENS FIT ASSESSMENT

This will consist of two separate assessments:

1. Centration: Perfectly centred,

Slightly decentred,

Markedly decentred but corneal coverage,

Unacceptable decentration showing corneal exposure.

2. Confirmation whether the lens fit is clinically acceptable: Yes / No.

6 MONITORING PROTOCOL ADHERENCE

Adherence to study visit windows, lens wearing schedule, and time windows around other data collection points (i.e. subjective ratings) will be monitored by CORE. Deviations from the study plan as described in the protocol will be reported in the study report. As described in Section 13.4, major protocol deviations will be reported to the Sponsor and Sterling Institutional Review Board within 10 days of becoming aware of them (as per Sterling Institutional Review Board guidelines).

7 POTENTIAL RISKS AND BENEFITS TO HUMAN PARTICIPANTS

There may be no direct benefits to the subjects in this study. Participation in a study may contribute to scientific research information that may be used in the development of new contact lens products. The subjects will receive an examination of the front part of their eyes and may have the opportunity to try a different type of soft contact lenses and/or different lens care products at no cost to them. The contact lens materials used in this study are commercially available as daily wear. This study will investigate participants' wearing schedule intended for daily wear (NOT extended wear), similar to the average wearing time of 10-16 hours for daily wear lenses.

All lenses used in this study are IDE exempt under 21 CFR 812.2(c)2.

The habitual lens and the two study contact lens types will be worn as per their approved use; on a daily wear, monthly-replacement basis. When contact lenses are worn on a daily wear basis there is a small risk of an adverse event compared to not wearing contact lenses. When contact lenses are worn on an extended wear basis, there is a significantly increased risk of an adverse reaction compared with wearing contact lenses on a daily wear basis.

Adverse events and/ or complications in daily wear of soft contact lenses can occur (e.g.: inflammation and infection). Complications that may occur during the wearing of contact lenses include discomfort, dryness, aching or itching eyes, excessive tearing, discharge, hyperemia and variable or blurred vision. More serious risks may include pain, photophobia, iritis, corneal edema or eye infection. Although contact lens-related infections are very infrequent, the possibility does exist. The incidence of infection due to day-wear soft lenses is 0.035%. Almost always an infection will occur only in one eye. This risk is assumed by 35-million Americans who currently wear contact lenses and only current soft lens wearers will be recruited for this study.

A dye (fluorescein) normally used for eye examinations is being used in this study. Although rare, it is possible to have an allergic reaction to the dye. Participants will be asked if they have a known allergy or sensitivity to fluorescein.

The assessments conducted in this study are routine clinical procedures and they include auto-refraction, auto-keratometry, visual acuity, anterior ocular health assessment, and contact lens fitting will be used. In addition, high magnification imaging of the lens fit may be made using 35 mm or digital cameras. Patients will be monitored frequently until the end of the study to reduce the occurrence of adverse or potential adverse events. Patients will be given instructions from their investigator regarding early symptoms and signs of adverse events.

8 ADVERSE EVENTS

See CORE SOP012 for a description of all adverse events, including management and reporting. An 'adverse event' refers to any undesirable clinical occurrence in a participant, whether it is considered to be device-related or not. Adverse events (AE) may be classified as 'unanticipated adverse device effects,' 'serious adverse events,' 'significant adverse events,' or 'non-significant adverse events,' as defined below, Table 5.

A number of conditions may result in temporary suspension until resolution. These include corneal infiltrates, corneal staining, limbal injection, bulbar injection or tarsal conjunctival abnormalities.

Table 4: Classification of types of adverse event

Classification	Definition
Serious Adverse Event	Those events that are life-threatening, or result in permanent impairment of a body function, or permanent damage to a body structure or necessitate medical (therapeutic) or surgical intervention to preclude permanent impairment of a body function or permanent damage to a body structure.
Significant Adverse Event	Those non-serious adverse events that occur with contact lens usage that are not sight-threatening but are usually symptomatic and may warrant therapeutic management and /or temporary or permanent discontinuation of contact lens wear.
Non-Significant Adverse Events	Those less severe non-serious adverse events that occur with contact lens usage that are not sight-threatening, may or may not be symptomatic and may warrant palliative management, such as ocular lubricants or temporary interruption of contact lens wear.
Unanticipated Adverse Device Effect	Adverse events in a study that were not previously identified in the protocol in terms of nature, severity, or degree of incidence. An Unanticipated Serious Adverse Device Effect is an unanticipated adverse event that is serious in nature and caused by or associated with the device and is considered reportable.

AE classification, coding (for reporting to the sponsor) and reporting details, plus examples, are provided in Table 6.

Table 5: Contact lens adverse event classification, coding and reporting guide

Code	Condition	Reporting					
Serious							
01	Presumed infectious keratitis or infectious corneal ulcer						
02	Permanent loss of ≥ 2 lines of best spectacle corrected visual acuity (BSCVA)	For all serious					
03	Corneal injury that results in permanent opacification within central cornea (6mm)	AEs:					
04	Uveitis or Iritis (e.g. presence of anterior segment inflammation as described in ISO 11980, Annex B)	Notify sponsor as soon as possible, within 24 hours;					
05	Endophthalmitis						
06	Hyphema	Ethics Board reporting will be					
07	Hypopyon	within 24 hours as per					
08	Neovascularization within the central 6mm of cornea	requirements					
00	Other serious event						
Signific	Significant Adverse Events						

11	Peripheral (outside central 6mm), non-progressive, non-infectious ulcer		
12	Symptomatic corneal infiltrative event		
13	Superior epithelial arcuate lesions (SEALs) involving epithelial split		
14	Corneal staining ≥ dense coalescent staining up to 2mm in diameter (e.g. moderate, ISO 11980 grade 3)	Notify sponsor as soon as possible, within 5 working days; Ethics Board reporting as per requirements	
15	Corneal neovascularization ≥ 1.0mm vessel penetration (e.g. ≥ ISO 111980 Grade 2), if 2 grade change from baseline		
16	Any temporary loss of ≥ 2 lines BSCVA for ≥ 2wks		
17	Any sign and/or symptom for which participant is administered therapeutic treatment or which necessitates discontinuation of lens wear for ≥ 2 weeks		
10	Other significant event		
Non-significant Adverse Events			
21	Conjunctivitis (bacterial, viral or allergic)		
22	Papillary conjunctivitis if ≥ mild scattered papillae/follicles approximately 1mm in diameter (e.g. ISO 11890 Grade 2), if 2 grade change from baseline	Notify sponsor as soon as possible,	
23	Asymptomatic corneal infiltrative events	within 5 working days; Ethics Board reporting as per requirements	
24	Any sign and/or symptom for which temporary lens discontinuation for > 1 day is recommended (if not already classified)		
20	Other sign and/or symptom warranting classification as a non-significant adverse event		

8.1 NORMAL OR ADAPTIVE SYMPTOMS

Transient symptoms such as end-of-day dryness, lens awareness, itching or burning or other discomfort may occur with contact lens wear and may occasionally reduce wearing time. These are not reported as adverse events unless in the investigator's opinion they are unexpected in nature, severe or have a high rate of occurrence.

8.2 PROCEDURES FOR ADVERSE EVENTS

Treatment of an adverse event will depend on its nature and severity. Based on the clinical judgment of the investigator the participant may be managed at the practice or referred to another eye care practitioner for treatment. The investigator will attempt to determine whether the reaction is related to the test device or a result of other factors. An adverse event form will be completed

[figure not shown]
for each adverse event. If both eyes are involved, a separate adverse event form will be completed *for each eye*. Whenever possible, the adverse event will be photo-documented.

Expenses incurred for medical treatment as part of study participation will be paid by the sponsor (bills and prescription receipts kept). The participant must be followed until resolution or no further change is anticipated and/or referred for further care with the appropriate health care professional and/or recorded as being under appropriate health care as per investigator's discretion. A written report will be completed indicating the subsequent treatment and resolution of the condition.

8.3 REPORTING ADVERSE EVENTS

All potential Serious Adverse Events and Unanticipated Adverse Device Effects that are related or possibly related to participant's participation will be reported to CORE's lead study coordinator (details below) and also to the sponsor (details below) within 24 hours of the investigator becoming aware of the event. The site's Principal Investigator will also report the event to Sterling IRB within 10 days of becoming aware of the Serious or Unanticipated event, using the Reportable Events Form. All fatal or life-threatening events will be reported immediately to the IRB.

Significant and Non-Significant Adverse Events will be reported to CORE's lead study coordinator and the sponsor as soon as possible, but no later than 5 working days after the occurrence. Each site's Principal Investigator will report the event to the IRB as per IRB requirements (by fax, mail/delivery, phone, or email).

Details of all adverse events will be included in the study report.

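### Section 8.3 limits 24-hour reporting of serious adverse events to those related or possibly related to participation, while Table 5 requires 24-hour sponsor notice of all serious events

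*Combined protocol and SAP*

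**What the plan says.** Three places in the protocol decide which serious events are reported quickly. (Table numbers here follow the captions; the running text of Section 8 cites these tables one number higher.)

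- **Section 8, definition.** An adverse event is "any undesirable clinical occurrence in a participant, whether it is considered to be device-related or not".
- **Table 5, serious events.** The reporting cell is headed as applying to all serious AEs and says "Notify sponsor as soon as possible, within 24 hours". The same cell gives 24 hours, as per requirements, for the Ethics Board.
- **Section 8.3.** The scope is set by this wording: "All potential Serious Adverse Events and Unanticipated Adverse Device Effects that are related or possibly related to participant's participation will be reported". The recipients are CORE's coordinator and the sponsor, and the limit is "within 24 hours of the investigator becoming aware of the event". As for the IRB, the lead investigator at each site is to "report the event to Sterling IRB within 10 days of becoming aware of the Serious or Unanticipated event". Two further sentences carry no relatedness condition: "All fatal or life-threatening events will be reported immediately to the IRB", and "Details of all adverse events will be included in the study report".

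For the lower classes, Section 8.3 says "Significant and Non-Significant Adverse Events will be reported to CORE's lead study coordinator and the sponsor as soon as possible", with an outer limit of 5 working days and no relatedness condition in that sentence.

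**The concern.** A site has two instructions for the same event. Under Table 5, a serious event that the site thinks unrelated to participation must reach the sponsor within 24 hours. Under 8.3, it need not be sent to CORE or the sponsor on any stated clock. A site that follows 8.3 to the letter can withhold a notice that Table 5 requires.

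The literal effect of 8.3 also runs against severity, because a non-serious event has a timed route to CORE and the sponsor and an unrelated serious one does not. In addition, the opinion on relatedness decides whether the 24-hour notice goes out. Section 14 has all serious events reviewed by CORE's Director and/or Head of Clinical Research. That review is a prompt check on the site's opinion only if the event reaches CORE promptly, whatever the site thought of its cause.

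**Working it through.** No arithmetic applies. The check sets the passages side by side and follows one case through them: a serious event that the site judges unrelated to participation.

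**Step 1: does 8.3 send it to CORE and the sponsor within 24 hours?** No, on the natural reading. The clause follows both event types in the sentence and so conditions both.

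**Step 2: does another sentence of 8.3 send it to them?**
- The 5-working-day sentence does not. It covers Significant and Non-Significant events, and Table 4 defines both classes as non-serious.
- The 10-day IRB sentence refers back to the event just described, so it appears to carry the same condition. In any case it goes to the IRB.
- The sentence on fatal or life-threatening events applies without a condition, but it also goes only to the IRB. Under Table 4, events can be serious through permanent impairment or damage, or through intervention to prevent it, without being life-threatening. This sentence does not reach those.
- The study-report sentence covers the event, but only at the end of the study.

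**Step 3: does Table 5 send it?** Yes: to the sponsor within 24 hours, and to the Ethics Board within 24 hours as per requirements.

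**Step 4: do other sections bring it to CORE or the sponsor?**
- Section 8.2 requires an adverse event form for each event. Sections 5.2.2 and 12.2 have visit documents sent to CORE the same day or within two days of the visit. That the adverse event form travels with them is an inference. The limit runs from a study visit, and the recipient is CORE.
- Section 14 has sites include adverse events in status reports, which CORE collates for the sponsor. The reports are described as regular or frequent, with no set interval.
- Section 14 also requires the review of all serious events, with no time limit.

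**Step 5: who judges relatedness?** Section 8.3 does not say. Its clock runs from the investigator's awareness, Section 8.2 has the investigator attempt to determine relation to the test device, and Section 5.1.3 says that investigators cannot be masked. That the unmasked site investigator makes the call is therefore a fair inference, though 8.3 does not state it.

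**Result.** For this case Table 5 requires sponsor notice in 24 hours and 8.3 sets no time for notice to CORE or the sponsor. For an unrelated event classed as Significant or Non-Significant, 8.3 sets 5 working days.

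**The case against.** The best defence is that 8.3 does not stand alone.

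- **The threshold is low.** It covers potential serious events and includes those possibly related, and relation is to participation as a whole, which is wider than the device. Most ocular events during lens wear would pass it. This stands and makes the gap narrow, but a condition remains that Table 5 does not have.
- **Other routes exist.** Table 5, the two-day rule for visit documents, status reports, CORE's review and the study report all apply. This stands too. However, the two-day rule sets no clock for an event learned of between visits, and Table 5 is one side of the conflict, so it cannot also resolve it.
- **The clause might attach to Unanticipated Adverse Device Effects alone.** That reading removes the conflict. It is grammatically possible but strained, and a 24-hour safety rule should not depend on it.
- **The lower classes are not free of any condition.** Table 4 describes both as events occurring with contact lens usage. That is a mild association test within the definition, and it blunts the contrast without removing it.
- **CORE SOP012 may settle the matter.** Section 8 refers to it for management and reporting. It is not among the documents, so this cannot be checked.

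A reader might go further and infer that an unrelated serious event has no reporting route in 8.3, or that nobody outside the site ever sees the relatedness call. The documents do not support either. Section 8.3 itself sends fatal or life-threatening events to the IRB at once and puts every event in the study report, and Section 14 has all serious events reviewed at CORE.

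**Conclusion.** The contradiction is real and lies within the protocol: 8.3 conditions 24-hour reporting of serious events on relatedness and Table 5 does not. The consequence is limited to whether, and how soon, CORE and the sponsor are told of a serious event judged unrelated. No event is lost from the final record if the study-report sentence is followed. The sample size and the primary comparison are unaffected. It should be corrected because two conflicting instructions govern a 24-hour safety notice.

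No number can be put on it. A reader might reach for the 0.035% infection incidence in Section 7, but that figure has no time unit and concerns lens-related infection, the kind of event least likely to be judged unrelated to participation.

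The conclusion rests on three assumptions: the clause in 8.3 conditions both event types; the Table 5 cell, which is broken in the extracted text, reads as one entry for all serious events; and SOP012 does not override 8.3.

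**What to change.** Delete the relatedness clause from the 8.3 sentence on reporting serious events to CORE and the sponsor, so that its scope matches Table 5. If the clause was meant for Unanticipated Adverse Device Effects only, split the sentence so that it says so.

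Do not move the condition to the IRB sentence without also reconciling Table 5, whose Ethics Board entry sits under the same all-serious-events heading. The time limits need reconciling in the same edit: Table 5 gives 24 hours for the Ethics Board and 8.3 gives 10 days for the IRB. Check SOP012 for consistency with the result.

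The cost is one sentence of protocol text and an occasional extra 24-hour notice. No visit, analysis or sample-size figure changes.

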9 DISCONTINUATION FROM THE STUDY

Participants may be discontinued at the discretion of the investigator or sponsor in consideration of participant safety or protocol compliance, or at discretion of the participant. Participants discontinued from a study will be reimbursed for their active involvement in the study (including the initial screening visit and all lens fitting visits). Upon discontinuing, a participant will be offered the option of their data being withdrawn from future statistical analysis. The following is a list of possible reasons for discontinuation from the study:

- Screening failure: Participants will be discontinued if they do not meet the inclusion and exclusion criteria outlined in section 5.2.3.
- Unacceptable performance with products to be used in study: Participants may be discontinued if they are unable to achieve acceptable comfort and /or vision with the study products.
- Positive slit lamp finding: Participants may be permanently discontinued from the study depending on the severity of the condition and on the judgement of the investigator.
- Adverse event: If a participant experiences an adverse event during the study they may be discontinued based on the clinical judgement of the investigator.
- Symptoms: If the participant has persistent symptoms they may be discontinued based on the clinical judgement of the investigator.
- Disinterest, relocation or illness: The participant may choose to discontinue due to reasons within or beyond their control.
- Violation of protocol or non-compliance: The participant will be discontinued if they are unable or unwilling to follow the protocol specified visit schedules and/or study procedures.
- Instillation of topical ocular medication: The participant will be discontinued if they elect
 to use a topical ocular medication during the study unless that topical ocular medication
 is prescribed for a limited duration (less than two weeks) to treat a transient condition; in
 this case the participant may remain an active participant (at the discretion of the
 investigator) after stopping topical ocular medication following resolution of the ocular
 condition).

- Lost to follow-up: The participant will be discontinued if they cannot be contacted and do
 not return for a final exit visit, and if the investigator has made a reasonable effort to
 contact the participant for a final study visit.
- Premature termination of the study by the sponsor, CORE or Sterling IRB.

A discontinuation form, stating the reason for discontinuation will be completed, which requires the signatures of both the participant and the investigator except where the participant is lost to follow-up in which case only the signature of the investigator is required.

When a participant choses to discontinue from the study they will be given the opportunity to withdraw their data from the statistical analysis. This choice will be captured on the discontinuation form.

All discontinuations including their reasons will be included in the final report.

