12 STATISTICAL ANALYSIS AND DATA MANAGEMENT

12.1 STATISTICAL ANALYSIS

All data will be analyzed by CORE at the University of Waterloo. Descriptive statistics will be provided on information regarding demographics (e.g. age, sex).

Differences between lenses and differences over time will be compared using either Paired t-tests or Wilcoxon matched pairs. Analysis will be conducted using Statistica 13 and SPSS 27.0. The appropriate tests will be selected based on tests of normality - non-parametric tests will be used for data not showing a normal distribution. Means and standard deviations will be provided for each variable. Medians will be provided for those variables analyzed with non-parametric tests. For all tests, values of p<0.05 will be considered significant.

For assessments conducted for each eye separately, the right eye will be used for analysis. If a general difference is found (paired t-test / Wilcoxon matched pairs) between OD and OS, a comment will be provided. Visual acuity data will be analyzed using OU.

For the agreement and preference data, binomial testing will be used to analyze the count data of subjective answers: For agreement analysis, "strongly agree" and "agree" will be combined into a single "agreement" category; similarly, "strongly disagree" and "disagree" will be combined into a single "disagreement" category. The number of "neither agree/disagree" ratings will be evenly distributed to these two categories on the basis they would be equally likely to choose either. Comments regarding the clinical relevance of differences in subjective ratings will be based on the conclusion by Navascues-Cornago et al.³ that on a scale of 0-100, differences greater or equal to 7 points would generally represent a difference that a patient would notice.

Equivalence testing will be conducted for ratings of comfort, dryness, vision clarity and overall satisfaction. Testing will be performed using Mintab 21.4. A value of 7 will be used as the margin for equivalence³.

Equivalence testing of visual acuity will be conducted using an equivalence margin of 0.10 logMAR.⁴⁻⁶

Additional analysis will determine the number of lenses and fit attempts needed to determine the optimal lens prescription.

Table 6: Statistical procedures

Variable	Analysis	Statistical test
Ratings: Likert & Preference	Comparison between study days	Freidman ANOVA
	and/or between contact lenses per	Wilcoxon matched pairs test

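### The lens comparison is a completers-only paired analysis that ignores period and discards single-period ratings, and no planned analysis checks whether losses depend on the lens

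*Combined protocol and SAP*

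**What the plan says.** Section 12.1 gives the main method: "Differences between lenses and differences over time will be compared using either Paired t-tests or Wilcoxon matched pairs". Table 6 in the same section adds Friedman ANOVA and repeated-measures ANOVA. The primary outcome (Section 3) is the 0-100 rating of handling for insertion after one month, collected at Visits 1-3 and 2-3.

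Section 5.3.1 randomizes up to 60 participants so that at least 53 complete.

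Section 9 lists reasons for leaving. Some concern the lens, for example: "Participants may be discontinued if they are unable to achieve acceptable comfort and /or vision with the study products". Persistent symptoms, slit lamp findings and adverse events are also listed. Others need not concern the lens. Under disinterest, relocation or illness it says: "The participant may choose to discontinue due to reasons within or beyond their control". Non-compliance and loss to follow-up are listed too.

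On data already given, Section 9 speaks twice. For anyone discontinuing: "Upon discontinuing, a participant will be offered the option of their data being withdrawn from future statistical analysis". Later, for a participant who chooses to leave: "they will be given the opportunity to withdraw their data from the statistical analysis". It also commits to reporting: "All discontinuations including their reasons will be included in the final report".

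Section 5.5 refers to an analysis population, but no section defines one. There is no rule for incomplete pairs and no sensitivity analysis for losses.

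**The concern.** A paired test uses only participants with both 1-month ratings. Someone who leaves during Pair #1 has no primary rating. Someone who leaves during Pair #2 has a valid Visit 1-3 rating, which the test throws away. Over-recruiting from 53 to 60 protects power, but it does not protect against losses that depend on the lens being worn.

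The secondary results are exposed in the same way. Section 12.1 plans equivalence tests, with a margin of 7 units, for ratings that include comfort and vision clarity. Poor comfort or vision is also a stated ground for discontinuation. If people who could not tolerate one lens are missing, the observed difference on these ratings could move towards zero and make equivalence easier to declare. The preference questionnaire is given only at Visit 2-3 (Section 5.5.10), so it too comes from completers alone.

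The report will list discontinuations with reasons, but nothing requires a breakdown by lens or period. A reader could not readily see whether losses were uneven.

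**Working it through.** **1. The plan's own figure.** Inputs from Section 5.3.1: difference 5, SD 12.7, two-sided alpha 0.05, power 80%. Taking 12.7 as the SD of the within-participant difference, the noncentral t distribution gives n = 53 with power 80.3%, which matches the plan. The documents do not say that 12.7 is the SD of differences, but of the variants tried only this reading gives 53. The loss allowance is (60 - 53)/60 = 7/60 = 11.7%.

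**2. Who contributes to the paired test.**
- Leaves during Pair #1: no 1-month rating, so not in the test.
- Leaves during Pair #2: one rating (Visit 1-3), discarded.
- Completes both: used.

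Withdrawing data therefore changes almost nothing in the paired test, because early leavers are already outside it. It does change what a single-period analysis could use.

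**3. Size of a possible bias.** Let completers average 5 units, with positive values favouring the lens they rate higher. Let the 7 lost have averaged D had they been rated. D is an assumption; the documents give no value.

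Mean over all 60 = (53 x 5 + 7 x D)/60

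Completer estimate minus that mean = 7/60 x (5 - D)

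| Assumed D | Mean over all 60 | Completer error |
|---|---|---|
| +10 | (265 + 70)/60 = 5.58 | -0.58 |
| +5 | (265 + 35)/60 = 5.00 | 0 |
| 0 | 265/60 = 4.42 | +0.58 |
| -10 | (265 - 70)/60 = 3.25 | +1.75 |
| -20 | (265 - 140)/60 = 2.08 | +2.92 |

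What matters is the gap between completers and those lost. Multiplying 7/60 by the leavers' own difference would be right only if completers averaged zero.

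**4. Period.** With n1 and n2 completers in the two orders, the paired mean equals the lens effect plus (n1 - n2)/(n1 + n2) times the period difference. If 60 were split 30/30 (assumed) and all 7 losses fell in one order, the split would be 30/23 and the weight 7/53 = 0.13. A model with a period term removes this.

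**5. What single-period ratings add.** Suppose all 7 leave during Pair #2, split evenly by order (3.5 per lens on average). The paired variance is 12.7²/53, a standard error of 1.744. For within-person correlation r, the variance of one rating is 12.7²/(2(1 - r)), and the 7 single ratings give an independent contrast with variance 2/3.5 times that. Combining the two by inverse variance lowers the variance by 6.2% at r = 0, 3.2% at r = 0.5 and 1.9% at r = 0.7. The gain in precision is small. The model is worth having mainly for its period term, its use of all available ratings and its stated population.

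**The case against.** The strongest reply is that this is a short crossover of marketed lenses in habitual multifocal wearers, and the plan is more open than it first looks. Several stronger readings are tempting, and the documents do not support them.

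- **That leavers' data are deleted.** Section 9 speaks of withdrawal from statistical analysis. It is an option, and Section 12.2 keeps study data for at least 25 years.
- **That only satisfied participants are analysed.** Several reasons for leaving need have nothing to do with satisfaction, discontinuation for poor performance is discretionary, and a dissatisfied participant can finish and rate low. Poor insertion handling, the primary outcome, is not itself a listed reason. Both lenses must be tried on eye in final power before either is dispensed (Section 5.5.1), which screens out some intolerance.
- **That losses would leave no trace.** Discontinuations and their reasons are reported, and Section 8.3 adds: "Details of all adverse events will be included in the study report". Only the breakdown by lens and period is missing.
- **That the result would reverse.** From a completer mean of 5, the 7 lost would have to average below -(53 x 5)/7 = -37.9 units, about three times the SD of 12.7.

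It can also be said that a mixed model does not cure lens-related loss, because the lens that drove someone out stays unrated. That is correct, and it is why a table by lens and a restricted sensitivity analysis are needed beside the model. The repeated-measures ANOVA in Table 6 does not answer the point either: its variable label is not legible in the available text, and as conventionally run it also drops incomplete participants.

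What survives these replies is the completers-only comparison, the missing period term, and the absence of any check on losses by lens.

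**Conclusion.** The point holds as a worthwhile, inexpensive improvement, not as evidence that the result will be biased. The plan accepts up to 7 losses in 60, names some lens-related reasons for them, and compares lenses only among those with both ratings. Over the assumed range of D from +10 to -20, the completer estimate of 5 differs from the all-randomized mean by -0.58 to +2.92 units. The error is zero if those lost resemble completers. Losses unrelated to the lens or the ratings would cost power without necessarily biasing the difference.

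These figures rest on three assumptions: all 7 allowed losses occur, completers average the 5-unit target, and D takes the values shown. Neither the size nor the direction of any bias can be found from the documents. The data-withdrawal option is a secondary issue: it matters mainly because it can take Pair #1 ratings away from an analysis able to use them.

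**What to change.** 1. In Section 12.1, analyse 1-month ratings in a mixed model with lens and period as fixed effects and participant as a random effect. Include every randomized participant with at least one 1-month rating whose data are not withdrawn, and name this as the analysis population. State that the model does not recover a rating for a lens that was never rated.
2. Tabulate discontinuations and data withdrawals by lens worn, period and reason. The discontinuation form already records the reason and the withdrawal choice.
3. Add a sensitivity analysis over a range of assumed unfavourable scores, only for participants whose recorded reason relates to the lens worn. Do not apply it to relocation, illness or similar reasons, which would penalise a lens for unrelated losses. For someone who left during Pair #2 the assumed score joins the Visit 1-3 rating; for someone who left during Pair #1 it enters as a single-period value.
4. Reconcile the two statements in Section 9 on who is offered data withdrawal: anyone who discontinues, or only those who choose to.

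The cost is analysis text, one table and one extra analysis, with no new visits, participants or data items. The downside is a little more analysis work and some reliance on model assumptions. Fix the rules before the interim results at about 30 completers (Section 16) are seen, so that the handling of losses cannot appear to follow from them.
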